9.7.2 Statistical methods

This is a purely descriptive study and the statistical analyses and presentations do not include any testing of pre-specified hypotheses. All analyses and presentations will be based on the Full Analysis Set.

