8.1 Objectives

8.1.1 Primary objective

The aim of this non-interventional study is to investigate the incidence of specific adverse drug reactions associated with the use of recombinant factor XIII (rFXIII) in patients with congenital FXIII A-subunit deficiency, comprising anti-FXIII antibodies, allergic reactions, embolic and thrombotic events and lack of therapeutic effect.

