9.3.3.2 Blood sampling

Blood samples collected in this study are samples taken as part of routine treatment established by the Physician as follows:

- Anti-FXIII antibody (see section 9.3.3.2).
- FXIII activity (optional) (see section 9.3.3.2).
- Blood samples for anti-FXIII antibody assessment should be taken, at Visit 1 and at a visit to be conducted 1 year after the patient entry into the study for patients consenting to testing in countries where the collection of blood samples for anti-FXIII antibody assessment is possible within the confines of a non-interventional study (see section 9.3.3.2).

Protocol	Date:	02 February 2016	Novo Nordisk

 Study ID: NN1841-3868
 CONFIDENTIAL
 Version: 2.0

 UTN: U1111-1131-1558
 Status: Final Page: 36 of 65

The Physician is strongly encouraged to draw blood samples for FXIII activity and anti-FXIII antibodies if any indication of lack of therapeutic effect emerges.

Data collection should happen in conjunction with all otherwise scheduled visits to the clinic. Time and date of collection should be recorded in the CRF.

Blood samples for anti-FXIII antibodies (Central laboratory)

When judged necessary by the treating Physician, blood samples will be drawn for analysis of anti-FXIII antibodies prior to any planned rFXIII injection.

Sample for antibody analysis may be taken at any visit.

Additionally, samples for antibody analysis should be taken, at Visit 1 and at a visit to be conducted 1 year after entry of the patient into the study, for patients consenting to testing, in countries where the collection of blood samples for anti-FXIII antibody assessment is possible within the confines of a non-interventional study.

When lack of therapeutic effect is indicated by bleeding or laboratory findings, the Physician is strongly encouraged to sample for anti-FXIII antibody detection as this is part of normal practice.

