9.7.1 Evaluability of patients for analysis

There will only be a Full Analysis Set in the study, comprising all patients who have entered into the study fulfilling the inclusion and exclusion criteria and having received at least one administration of rFXIII containing product in the study period. The Full Analysis Set will be identical to the Safety Analysis Set.

 Study ID: NN1841-3868
 CONFIDENTIAL
 Version: 2.0

 UTN: U1111-1131-1558
 Status: Final

 EU PAS No.: ENCEPP/SDPP/3687
 Page: 45 of 65

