9.7.2.1 Primary endpoint

The primary endpoint comprises specific adverse drug reactions in terms of anti-FXIII antibodies, allergic reactions, embolic and thrombotic events and lack of therapeutic effect occurring from first study related activity after signing the informed consent to the end of patient's participation in the study.

The referred specific adverse drug reactions of the primary endpoint (anti-FXIII antibodies, allergic reaction, embolic and thrombotic events and lack of therapeutic effect) will be summarised, displaying the number of reactions and the number and percent of patients experiencing the reaction relevant within system organ class and Medical Dictionary for Regulatory Activities (MedDRA) preferred term. Assessments of anti-FXIII antibodies will be provided by the central laboratory. The endpoint will be presented for all patients as well as by special populations, comprising children, elderly, pregnant and lactating women, and patients with renal insufficiency.

All the specific adverse drug reactions will further be listed with patient ID, site, age, preferred term, date of first dose, date of onset, date of arrest, severity, if it is serious or not, relationship to study drug, action, and outcome.

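### The anti-FXIII antibody percentage uses the Full Analysis Set although testing is voluntary and country-limited, so it is at best a lower bound on incidence

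*Protocol*

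**What the plan says.** **Objective.** Protocol section 8.1.1 sets out to investigate the incidence of four kinds of adverse drug reaction, with anti-FXIII antibodies named first.

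**Denominator.** Section 9.7.1 says "There will only be a Full Analysis Set in the study". Membership requires eligibility and "having received at least one administration of rFXIII containing product in the study period"; no antibody sample is needed. Section 9.7.2 adds "All analyses and presentations will be based on the Full Analysis Set".

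**Statistic.** Section 9.7.2.1 summarises every primary component by the number of reactions and "the number and percent of patients experiencing the reaction". For antibodies it adds "Assessments of anti-FXIII antibodies will be provided by the central laboratory".

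**Who is tested.** Under section 9.3.3.2 the Visit 1 and year-1 samples are "for patients consenting to testing in countries where the collection of blood samples for anti-FXIII antibody assessment is possible" within a non-interventional study. Sections 9.3, 9.3.1.1 and 9.3.1.2 and the flow chart (Table 9-1, footnote 4) repeat these limits. Otherwise the rule is "When judged necessary by the treating Physician, blood samples will be drawn for analysis of anti-FXIII antibodies", with encouragement to sample when lack of effect is suspected. The end-of-study sample is optional (section 9.3.1.3).

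**The concern.** Allergic reactions, thrombotic events and lack of effect can be picked up by asking the patient at each contact, so all dosed patients are a reasonable denominator for them. An antibody without symptoms can be found only by drawing blood. Dividing antibody-positive patients by all dosed patients gives a never-tested patient the same arithmetic weight as one who tested negative.

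The reader of the report could not undo this. Section 9.7.3 summarises Visit 1 antibody results. After that, the summaries in sections 9.7.4.1 to 9.7.4.7 include FXIII activity but neither antibody results nor the number tested. The patient listing in 9.7.2.1 covers reactions only, so patients who tested negative and patients never tested look alike. Section 9.9 on limitations does not mention incomplete testing.

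At stake is whether the percentage for this component can be read as the incidence that the primary objective asks for. Section 9.3 says that the two scheduled samples were added at a regulator's request.

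**Working it through.** **Inputs from the protocol.** Anticipated minimum enrolment is 30 (section 9.5). It can be reproduced from the lower end of the European population and the stated uptake: 10% x 300 = 30. Taking 30 as the Full Analysis Set (FAS) assumes that every enrolled patient is dosed in the study.

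**Inputs the protocol does not give.** The fraction tested after exposure, f, and the true cumulative incidence, p. I take f from 40% to 80% and p of 3%, 5% and 10%, purely for illustration.

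**Step 1: one positive patient.** The FAS percentage is 1/30 = 3.3%. The percentage of those tested is 1/(30f). The ratio of the two is f, so the relative shortfall is 1 - f.

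| f (assumed) | Tested (30f) | Percent of FAS | Percent of tested | Shortfall 1 - f |
|---|---|---|---|---|
| 80% | 24 | 3.3% | 4.2% | 20% |
| 60% | 18 | 3.3% | 5.6% | 40% |
| 50% | 15 | 3.3% | 6.7% | 50% |
| 40% | 12 | 3.3% | 8.3% | 60% |

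**Step 2: expected FAS percentage.** If p is the same in tested and untested patients, and sampling finds every case among those tested, the expected FAS percentage is f x p.

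| True p (assumed) | f = 80% | f = 60% | f = 50% | f = 40% |
|---|---|---|---|---|
| 3% | 2.4% | 1.8% | 1.5% | 1.2% |
| 5% | 4.0% | 3.0% | 2.5% | 2.0% |
| 10% | 8.0% | 6.0% | 5.0% | 4.0% |

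The shortfall disappears only if every patient is tested or no untested patient has antibodies. The protocol ensures neither.

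**Step 3: the counting window.** Section 9.7.2.1 counts reactions from the first study activity after consent. Sections 9.3.3 and 11.3 start collection after the first in-study rFXIII dose, and section 11.3 sends ongoing events that began before that dose to concomitant illness. The fourth inclusion criterion (section 9.2.2) admits patients already exposed, so a Visit 1 sample can be positive. Under the 9.7.2.1 window that patient could be counted as incident; under 9.3.3 and 11.3 the patient would not. The first reading pushes the percentage up, so the lower-bound interpretation requires Visit 1 positives to be left out.

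**Step 4: would tested patients alone be enough?** No. A pooled set of everyone with any post-exposure sample includes samples drawn because the product seemed not to work. Those patients are more likely to be positive, so the pooled rate can be too high. The scheduled year-1 sample is the only post-exposure sample not selected by symptoms or by physician choice.

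**The case against.** **The divisor is inferred.** The protocol nowhere writes that untested patients are negative, and number-with-data conventions are often left to a statistical analysis plan. That is fair as to wording. But sections 9.7.1 and 9.7.2 allow one analysis set and apply it to all analyses. A plan that follows them has no other denominator available.

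**The size is unknown.** This stands. The 40-80% range is assumed. The protocol does not say which countries disallow sampling or how many patients will decline, and with near-complete testing the effect is small. The formula holds; its value here cannot be computed.

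**Precision.** A reader might infer that the plan also overstates precision, because an upper limit on 30 patients is tighter than one on those tested. The protocol does not support this as a fault in a planned output: it is purely descriptive, and section 9.7.2.1 plans no confidence interval.

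**Later antibodies.** A reader might infer that silent antibodies after year 1 cannot be seen. Section 9.3.3.2 permits a sample at any visit and section 9.3.1.3 an optional one at study end. They are under-detected, not undetectable.

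**Visit 1 positives.** Sections 9.7.3 and 11.3 already handle these in part. What remains is the conflict with the window in 9.7.2.1, which could bias the percentage upward. It is therefore too strong to say without qualification that the rate is biased low.

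**Consequence.** No hypothesis test or decision threshold depends on this figure, and positives are listed by patient. That limits the harm to how the percentage is read.

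**Conclusion.** The point holds in a limited form. The protocol fixes an FAS denominator for a component that can be observed only in sampled patients, and it does not ask for the number tested after exposure. The resulting percentage is at best a lower bound on the incidence of treatment-emergent anti-FXIII antibodies, provided that Visit 1 positives are not counted as incident.

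The relative shortfall is 1 - f if incidence is equal in tested and untested patients and testing finds the cases among those tested. Under the assumed 40-80% tested, that is a shortfall of 60% to 20%. The direction needs only that some untested patients have antibodies; the amount cannot be derived from the protocol.

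**What to change.** In section 9.7.2.1, for the antibody component only:

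- (a) Print the numbers of patients tested and untested after first in-study rFXIII exposure.
- (b) Give as the main incidence the scheduled year-1 result among Visit-1-negative patients with a valid year-1 central-laboratory sample.
- (c) Report positives from triggered or discretionary samples separately, with the number of patients so tested.
- (d) Keep the FAS percentage, labelled as a lower bound.
- (e) Do not count Visit 1 positives as incident, and reconcile the counting window in 9.7.2.1 with sections 9.3.3 and 11.3.

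Keep the FAS for allergic reactions, embolic and thrombotic events, and lack of therapeutic effect. Sections 9.7.1 and 9.7.2 need a matching exception, because their present wording allows no other denominator.

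The cost is a short text change and a few table rows, with no new visits or samples. The downside is smaller denominators and a less favourable-looking rate. Item (b) describes the first year only and should be labelled so, not presented as incidence over the whole study period.

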9.7.2.1 Primary endpoint

The primary endpoint comprises specific adverse drug reactions in terms of anti-FXIII antibodies, allergic reactions, embolic and thrombotic events and lack of therapeutic effect occurring from first study related activity after signing the informed consent to the end of patient's participation in the study.

The referred specific adverse drug reactions of the primary endpoint (anti-FXIII antibodies, allergic reaction, embolic and thrombotic events and lack of therapeutic effect) will be summarised, displaying the number of reactions and the number and percent of patients experiencing the reaction relevant within system organ class and Medical Dictionary for Regulatory Activities (MedDRA) preferred term. Assessments of anti-FXIII antibodies will be provided by the central laboratory. The endpoint will be presented for all patients as well as by special populations, comprising children, elderly, pregnant and lactating women, and patients with renal insufficiency.

All the specific adverse drug reactions will further be listed with patient ID, site, age, preferred term, date of first dose, date of onset, date of arrest, severity, if it is serious or not, relationship to study drug, action, and outcome.

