			General updates since last protocol update 2 have been implemented in the updated protocol 3.	Please refer to page 3: Rationale for the Amendment
5	02 February 2016	Section 2 PASS information, Section 3 Responsible parties, Section 4.1 Title, Section 4.3 Primary endpoint, Secondary endpoints,	Recruitment period extended with 1 year to 17- May-2017. Definition of concomitant illness updated. Minor administrative changes implemented.	With the current recruitment rate it will not be possible to reach the anticipated number of 30 patients within the current recruitment period.

Protocol Study ID: NN1841-3868 UTN: U1111-1131-1558

EU PAS No.: ENCEPP/SDPP/3687

CONFIDENTIAL

02 February 2016 | Novo Nordisk 2.0 Final Date:

Version: Status: 16 of 65 Page:

Amendment or update no	Date	Section of study protocol	Amendment or update	Reason
		Section 4.5 Population, Section 4.8 Study size, Section 4.10 Milestones, Section 6 Milestones, Section 8.2.1 Primary endpoint, Section 8.2.2 Secondary endpoints, Section 9.1.1 Type of study, Section 9.1.2 Rationale for study design, Section 9.1.3 Treatment of patients, Section 9.3.2.7 Concomitant illnesses, Section 9.5 Study size, Section 9.7.2.2 Secondary endpoints.		Definition of concomitant illness aligned with other trials/studies in the project.

CONFIDENTIAL

Study ID: NN1841-3868 UTN: U1111-1131-1558 EU PAS No.: ENCEPP/SDPP/3687 Version: 2.0
Status: Final
Page: 17 of 65

6 Milestones¹

Milestone	Planned date
Start of data collection	17 May 2013
Defined as first entry of patient data	
Interim report 1	17 May 2015
Interim report 2	17 May 2017
End (or completion) of study	29 Jun 2019
Defined as the Last Patient Last Visit (LPLV)	
End of data collection	17 Aug 2019
Defined as the date from which the analytical dataset is completely available	
Registration in the EU PAS Register	28 May 2013
Final report of study results	28 Dec 2019
Planned completion of non-interventional study report	

Planned duration of recruitment period is 4 years after first patient first visit (FPFV) in the study.

All study visits should be performed according to normal local clinical practice. No additional visits should be conducted due to the participation in this study. It is recommended that assessment visits occur every one to six months depending on usual practice. The study will be terminated after 6 years; hereafter no more assessment visits will be performed.

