9.1.3 Treatment of patients

The treatment regimens will be in accordance with the approved product labelling in the country of residence of the patient, if rFXIII is used for other indications in patients with FXIII CD this information will also be collected. It is recommended that data collection happens in conjunction with otherwise scheduled visits to the clinic. Patients are expected to remain in the study for up to 6 years depending on time of enrolment.

The study medication used is the commercially available rFXIII (Coagulation Factor XIII A-subunit (recombinant)/INN name: catridecacog, 2500 IU (15 mg)). Administration will be according to the approved package insert (for further information see US PI, EU SmPC, or corresponding local prescribing information). The medication will not be supplied by Novo Nordisk. All direction for medication usage is solely at the discretion of the Physicians in accordance with their usual care guided by the provided product information (US PI and EU SmPC, or corresponding local prescribing information).

There will be no dispensing of any study medication as part of this study. No auxiliary dispensing materials or devices apart from those provided with the commercially available rFXIII product are expected to be used.

The decision to initiate treatment with commercially available catridecacog has been made by the patient/parent and the patient's treating physician before and independently from the decision to include the patient in this study.

For the collection of blood samples, tubes will be provided.

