9.2.4 Withdrawal criteria

- 1. The patient may withdraw at will at any time.
- 2. The patient's parent or patient's LAR may withdraw the patient at any time.

If antibodies to rFXIII product are detected, the treatment with rFXIII may be continued, interrupted or discontinued at the discretion of the Physician. It is strongly encouraged that the patients remain in the study and have regular follow-up visits for monitoring of antibodies until the level has diminished to below clinical significance or detection limit.

Interruption of treatment with rFXIII or termination of treatment with rFXIII is not a criterion for withdrawal from this study.

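### Section 9.7.2.1 answers an incidence objective with counts and a crude percent of patients over unequal follow-up of about 2 to 6 years, with no person-time denominator

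*Protocol*

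**What the plan says.** Protocol section 8.1.1 sets the primary objective: to "investigate the incidence of specific adverse drug reactions associated with the use of recombinant factor XIII" in four categories (anti-FXIII antibodies, allergic reactions, embolic and thrombotic events, lack of therapeutic effect). It does not say whether incidence means a proportion or a rate.

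Section 9.7.2.1 fixes the summary as "displaying the number of reactions and the number and percent of patients experiencing the reaction relevant within system organ class" and MedDRA preferred term, for all patients and for special populations, with a dated patient listing. The window covers reactions "occurring from first study related activity after signing the informed consent to the end of patient's participation in the study".

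The length of that window varies:
- Section 9.1.3: "Patients are expected to remain in the study for up to 6 years depending on time of enrolment".
- Section 6: "Planned duration of recruitment period is 4 years after first patient first visit (FPFV) in the study". The study stops at 6 years.
- Section 9.2.4: patients may leave at any time, and "Interruption of treatment with rFXIII or termination of treatment with rFXIII is not a criterion for withdrawal from this study".
- Section 9.7.1: the analysis set takes in anyone with at least one in-study administration.

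Section 9.7.2.2 plans an annualised rate for bleeding over the same window. Section 9.7.5 repeats the section 9.7.2 descriptions in two-yearly interim reports. Sections 9.2.6 and 9.3.3.2 schedule antibody samples at Visit 1 and at one year, for consenting patients in countries that allow it. Other samples are taken at the physician's judgement.

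**The concern.** When follow-up differs up to threefold by entry date, the percent of patients affected is not a risk over any defined period. It depends on the calendar of enrolment and on dropout as well as on the drug. A patient who has one dose and then years off rFXIII enters the denominator exactly as a patient with six years of monthly prophylaxis does.

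This is a matter of what the protocol fixes, not of what it leaves open: section 9.7.2.1 names the statistic. At stake is whether the main safety result can be read. A percent that grows with each report may look like an emerging signal when only time has passed, and a low percent may reflect late entry.

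**Working it through.** **Follow-up.** Section 9.5 gives an expected average participation of about 4.5 years, assuming constant recruitment over 4 years. Under constant recruitment the mean is (longest + shortest)/2:
- to 6 years after first patient first visit: (6.0 + 2.0)/2 = 4.0 years;
- to the planned last visit of 29 Jun 2019: (6.12 + 2.12)/2 = 4.12 years;
- to 17 Aug 2019, three months after the 6-year point: 4.25 years.

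The 4.5 is not reproduced. It matches a 3-year recruitment period, (6 + 3)/2. That is a separate point, so both values are carried below. The planned range of about 2 to 6 years holds either way.

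**Dependence of the percent on follow-up.** The protocol gives no event rate, so the rates λ here are assumptions. With a constant rate, the percent affected after t years is 1 − exp(−λt). Example at 2.5 per 100 patient-years: 1 − exp(−0.05) = 4.9% at 2 years and 1 − exp(−0.15) = 13.9% at 6 years.

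| Assumed rate per 100 patient-years | 2 years | 4 years | 6 years | Ratio, 6 to 2 years |
|---|---|---|---|---|
| 1 | 2.0% | 3.9% | 5.8% | 2.9 |
| 2.5 | 4.9% | 9.5% | 13.9% | 2.9 |
| 5 | 9.5% | 18.1% | 25.9% | 2.7 |
| 10 | 18.1% | 33.0% | 45.1% | 2.5 |

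**Drift across reports.** With even accrual over 4 years and no dropout, follow-up is spread evenly over 0–2 years at interim 1 (17 May 2015), 0–4 years at interim 2 (17 May 2017) and 2–6 years at the end. For follow-up spread evenly from a to b, the expected percent is 1 − [exp(−λa) − exp(−λb)]/[λ(b − a)]. At 2.5 per 100 patient-years:
- interim 1: 1 − (1 − exp(−0.05))/0.05 = 2.5%;
- interim 2: 1 − (1 − exp(−0.10))/0.10 = 4.8%;
- final: 1 − (exp(−0.05) − exp(−0.15))/0.10 = 9.5%.

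The percent nearly quadruples at an unchanged rate.

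**What a rate would show.** The anticipated minimum of 30 patients gives 30 × 4.0 = 120 patient-years, or 30 × 4.5 = 135 at the stated mean. Exact 95% intervals on 120 patient-years:
- 0 events: 0 (0 to 3.07) per 100 patient-years; the upper limit is 2.73 on 135;
- 1 event: 0.83 (0.02 to 4.64);
- 3 events: 2.50 (0.52 to 7.31).

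**Antibodies.** Here detection follows sampling, so the denominator problem is who was tested. The number tested is not given. If 15, 20 or 25 of 30 patients had a sample after Visit 1, one positive would be 1/15 = 6.7%, 1/20 = 5.0% or 1/25 = 4.0%, against 1/30 = 3.3% of all patients.

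**The case against.** A percent of patients with an event is itself a form of incidence, and section 8.1.1 does not promise a rate. The study is single-arm, plans no external comparison, and section 9.7.2 says "This is a purely descriptive study and the statistical analyses and presentations do not include any testing of pre-specified hypotheses". This stands: the plan is ill-suited to its objective but does not contradict it.

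Three stronger readings may tempt a reader, and the protocol supports none of them:
- That only percentages are shown. Counts of reactions and of patients are planned too, with a listing that carries first-dose and onset dates.
- That the four incidences can never appear. Section 9.7.2.1 names all four categories as what is summarised, and nothing excludes a patient total for each. Totals and confidence intervals are commonly left to a statistical analysis plan, which is not at hand, so their absence alone is no finding.
- That patients are double-counted. A patient with two different terms properly appears in two preferred-term rows. The text does not say that he or she counts twice at a higher level.

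Two technical objections also have force. Dividing antibody events by all exposure time would credit years without a test and could understate incidence. A constant rate is also only an assumption: the cohort mixes patients already on rFXIII with some starting it, and if risk concentrates early, the percent varies less with follow-up than the table shows.

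None of this supplies the missing time denominator. The protocol itself annualises bleeding, so the sponsor already accepts that unequal follow-up matters.

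**Conclusion.** The point holds as a recommended change to the stated primary summary. By design, follow-up ranges from about 2 to 6 years, is shorter after withdrawal, and may include time off rFXIII, yet section 9.7.2.1 gives no person-time denominator. Under assumed constant rates of 1 to 10 per 100 patient-years, entry date alone moves the expected percent 2.5- to 2.9-fold. At 2.5 per 100 and even accrual, the reported percent would go from 2.5% to 4.8% to 9.5% over the two interim reports and the final report.

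These sizes rest on assumed rates, a constant hazard, even recruitment and no dropout. The direction does not depend on the particular rate. The range of 2 to 6 years is the planned one only.

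**What to change.** In section 9.7.2.1:
1. State what incidence means for each category.
2. For allergic reactions, embolic and thrombotic events and lack of effect, report patients with a first event per 100 patient-years with an exact Poisson 95% interval. Use time in study from the first in-study dose to the first event in that category or the end of participation. That starting point matches sections 9.3.3 and 11.3, which collect events from the first in-study administration.
3. Give the same rate on time on rFXIII where dose dates allow, with a stated definition of on-treatment time that also covers use other than prophylaxis.
4. For anti-FXIII antibodies, report the number positive among patients with at least one sample after Visit 1, with an exact binomial interval, and show how many were sampled.
5. Keep the organ class and preferred term table as detail, and use the same layout in the interim reports.

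The cost is one extra summary table, with no added visit, sample or patient. The limitation is that on-treatment time will be incomplete where no diary is used, since section 9.3.5.1 supplies diaries only where they are routine. For that reason time in study should be the main denominator.
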